9.4.2. Secondary Analyses

The secondary efficacy endpoints are defined in Section 3.

IGA: Subjects' change from baseline in IGA score and the proportion of subjects with a 2-point decrease from baseline will be summarized by visit. Point-estimates and 90% confidence intervals for the differences between the experimental and vehicle arm at Week 16 will be presented. No formal hypothesis testing will be performed.

EASI: Subject's change from baseline/percent change from baseline will be summarized by visit. Point-estimates and 90% confidence intervals for the differences between the experimental and vehicle arm at Week 16 will be presented. No formal hypothesis testing will be performed.

Continuous endpoints will be presented as means and 90% confidence intervals.

Safety Analyses

AEs will be coded using the MedDRA coding dictionary and summarized by preferred term and treatment group. SAEs occurring pre-treatment and AEs and SAEs occurring during active treatment and post-treatment will be summarized separately. Separate summaries will be provided for all AEs, investigational product-related AEs, SAEs, AEs of special interest (including systemic reactions [allergic/type I hypersensitivity or Systemic Other] and local injection site reactions) and for AEs leading to permanent discontinuation of investigational product or withdrawal from the study. All laboratory parameters for clinical chemistry and hematology will be summarized and tabulated.

Summary statistics of pulse rate and systolic and diastolic blood pressure will be presented by visit.

Immunogenicity will be summarized using appropriate descriptive statistics.

Full details of planned analyses of safety endpoints will be included in the RAP.

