5.3. Screening/Baseline Failures

Screen failures are defined as subjects who consent to participate in the clinical trial but are never subsequently randomized. In order to ensure transparent reporting of screen failure subjects, meet the Consolidated Standards of Reporting Trials (CONSORT) publishing requirements, and respond to queries from Regulatory authorities, a minimal set of screen failure information is required including Demography, Screen Failure details, Eligibility Criteria, and Serious Adverse Events (See Section 7.4.1.5).

Subjects who are screen failures may be re-screened one time.

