8.2. Adverse Events of Special Interest Analyses

Adverse events of special interest (AESIs) are adverse events associated with the identified and potential risks of mepolizumab. AESIs reported by the investigator as anaphylaxis reactions, systemic reactions (further categorised by the investigator as either allergic (type I hypersensitivity) or other systemic reactions) and local injection site reactions are collected via targeted eCRF within the study.

The AESIs of opportunistic infections, malignancies, serious CVT events and serious ischemic events will be identified from a list of relevant preferred terms maintained within a project level reference dataset; created based on the latest version of the MedDRA dictionary available at the time of database freeze for this study.

Separate summary tables showing the number and percent of subjects with type of AESI, broken down by preferred term will be created if at least one event is reported for an AESI category. For each type of AESI a profile summary table will be produced containing information including, but not limited to, the number of occurrences of the event, event characteristics, time to onset, intensity, outcome and action taken if more than one event is reported for an AESI category.

Listings of AESIs identified by the investigator as anaphylaxis, allergic (type I hypersensitivity), other systemic reactions and local injection site reactions, opportunistic infections, malignancies, serious CVT events and serious ischemic events if more than one event is reported under each AESI category.

The details of the planned displays are provided in [Appendix 9](#): List of Data Displays and will be based on GSK data standards and statistical principles.

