12.9.6. Safety Tables

Safety: Tables					
No.	Population	IDSL / Example Shell	Title	Programming Notes	Deliverable
Adverse Events (AEs)					
3.1.	Safety	AE1	Summary of All On-Treatment Adverse Events by System Organ Class and Preferred Term	ICH E3	SAC
3.2.	Safety	AE1	Summary of All Post-Treatment Adverse Events by System Organ Class and Preferred Term	ICH E3	SAC
3.3.	Safety	AE15	Summary of Common (>=3%) On-Treatment Non-Serious Adverse Events by System Organ Class and Preferred Term (Number of Participants and Occurrences)	FDAAA, EudraCT	SAC
3.4.	Safety	AE1	Summary of Adverse Events Reported on the Day of Dosing by System Organ Class and Preferred Term		SAC
3.5.	Safety	AE1	Summary of On-Treatment Adverse Events by Highest Binding Antibody Result		SAC
Serious and Other Significant Adverse Events					
3.6.	Safety	AE16	Summary of On-Treatment Serious Adverse Events by System Organ Class and Preferred Term (Number of Participants and Occurrences)	FDAA, EudraCT	SAC
3.7.	Safety	AE16	Summary of Post-Treatment Serious Adverse Events by System Organ Class and Preferred Term (Number of Participants and Occurrences)	FDAA, EudraCT	SAC
3.8.	Safety	AE3	Summary of Fatal Serious Adverse Events by Overall Frequency		SAC
Adverse Events of Special Interest (AESI's)					
3.9.	Safety	SAF_T1	Summary of On-Treatment Adverse Events of Special Interest Reported by the Investigator as Meeting the Criteria for Anaphylaxis		SAC

CONFIDENTIAL

205050

Safety: Tables					
No.	Population	IDSL / Example Shell	Title	Programming Notes	Deliverable
3.10.	Safety	SAF_T2	Summary Profile of On-Treatment Adverse Events Reported by the Investigator as Meeting the Criteria for Anaphylaxis	Produced only if more than one AESI reported in this category.	SAC
3.11.	Safety	SAF_T1	Summary of On-Treatment Adverse Events of Special Interest Reported by the Investigator as Systemic Reactions - Allergic (Type I Hypersensitivity) and Other Systemic		SAC
3.12.	Safety	SAF_T2	Summary Profile of On-Treatment Adverse Events Reported by the Investigator as Systemic Reactions - Allergic (Type I Hypersensitivity) and Other Systemic	Produced only if more than one AESI reported in this category.	SAC
3.13.	Safety	SAF_T1	Summary of On-Treatment Adverse Events of Special Interest Reported by the Investigator as Systemic Reactions - Allergic (Type I Hypersensitivity)		SAC

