3.14.	Safety	SAF_T2	Summary Profile of On-Treatment Adverse Events Reported by the Investigator as Systemic Reactions - Allergic (Type I Hypersensitivity)	Produced only if more than one AESI reported in this category.	SAC
3.15.	Safety	SAF_T1	Summary of On-Treatment Adverse Events of Special Interest Reported by the Investigator as Systemic Reactions - Other Systemic		SAC
3.16.	Safety	SAF_T2	Summary Profile of On-Treatment Adverse Events Reported by the Investigator as Systemic Reactions - Other Systemic	Produced only if more than one AESI reported in this category.	SAC
3.17.	Safety	SAF_T1	Summary of On-Treatment Adverse Events of Special Interest Reported by the Investigator as Local Injection Site Reactions		SAC
3.18.	Safety	SAF_T2	Summary Profile of On-Treatment Adverse Events Reported by the Investigator as Local Injection Site Reactions	Produced only if more than one AESI reported in this category.	SAC
3.19.	Safety	SAF_T1	Summary of On-Treatment Adverse Events of Special Interest Categorized as Serious Cardiac, Vascular and Thromboembolic Events		SAC

Safety: Tables					
No.	Population	IDSL / Example Shell	Title	Programming Notes	Deliverable
3.20.	Safety	SAF_T2	Summary Profile of On-Treatment Adverse Events of Special Interest Categorised as Serious Cardiac, Vascular and Thromboembolic Events	Produced only if more than one AESI reported in this category.	SAC
3.21.	Safety	SAF_T1	Summary of On-Treatment Adverse Events of Special Interest Categorised as Serious Ischemic Events		SAC
3.22.	Safety	SAF_T2	Summary Profile of On-Treatment Adverse Events of Special Interest Categorised as Serious Ischemic Events	Produced only if more than one AESI reported in this category.	SAC
3.23.	Safety	SAF_T1	Summary of On-Treatment Adverse Events of Special Interest Categorised as Malignancies		SAC
3.24.	Safety	SAF_T2	Summary Profile of On-Treatment Adverse Events of Special Interest Categorised as Malignancies	Produced only if more than one AESI reported in this category.	SAC
3.25.	Safety	SAF_T1	Summary of On-Treatment Adverse Events of Special Interest Categorised as Opportunistic Infections		SAC
3.26.	Safety	SAF_T2	Summary Profile of On-Treatment Adverse Events of Special Interest Categorised as Opportunistic Infections	Produced only if more than one AESI reported in this category.	SAC
Laboratory: Chemistry					
3.27.	Safety	LB1	Summary of Chemistry Changes from Baseline	ICH E3 Includes Baseline values.	SAC

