12.9.12. ICH Listings

ICH: Listings					
No.	Population	IDSL / Example Shell	Title	Programming Notes	Deliverable
Subject Disposition					
1.	Screened	ES7	Listing of Reasons for Screen Failure	Journal Guidelines	SAC
2.	ITT	ES2	Listing of Reasons for Study Withdrawal	ICH E3	SAC
3.	ITT	SD2	Listing of Reasons for Study Treatment Discontinuation	ICH E3	SAC
4.	ITT	BL1	Listing of Participants for Whom the Treatment Blind was Broken	ICH E3	SAC
5.	ITT	TA1	Listing of Planned and Actual Treatments	IDSL	SAC
Protocol Deviations					
6.	ITT	DV2	Listing of Important Protocol Deviations	ICH E3	SAC
7.	ITT	IE3	Listing of Participants with Inclusion/Exclusion Criteria Deviations	ICH E3	SAC
Demographic and Baseline Characteristics					
8.	ITT	DM2	Listing of Demographic and Baseline Characteristics	ICH E3 Include Baseline Eosinophil Count and Fitzpatrick skin type	SAC
9.	ITT	DM9	Listing of Race	ICH E3	SAC
Prior and Concomitant Medications					
10.	ITT	CM3	Listing of Concomitant Medications	ICH E3	SAC
Exposure					
11.	Safety	EX3	Listing of Exposure Data	ICH E3	SAC

CONFIDENTIAL

205050

ICH: Listings					
No.	Population	IDSL / Example Shell	Title	Programming Notes	Deliverable
Adverse Events					
12.	Safety	AE8	Listing of All Adverse Events	ICH E3	SAC
13.	Safety	AE7	Listing of Participant Numbers for Individual Adverse Events	ICH E3	SAC
14.	Safety	AE2	Listing of Relationship Between Adverse Event System Organ Classes, Preferred Terms, and Verbatim Text	IDSL	SAC
15.	Safety	AE8	Listing of Adverse Events Leading to Withdrawal from Study / Permanent Discontinuation of Study Treatment		SAC
16.	Safety	AE8	Listing of Adverse Events Reported on the Day of Dosing		SAC
17.	Safety	AE8	Listing of All Adverse Events of Special Interest	Produced only if more than one AESI reported.	
All Laboratory					
18.	Safety	LB5	Listing of All Chemistry Laboratory Data for Participants with Any Value of Potential Clinical Importance	ICH E3	SAC
19.	Safety	LB5	Listing of All Haematology Laboratory Data for Participants with Any Value of Potential Clinical Importance	ICH E3	SAC
20.	Safety	LB14	Listing of Laboratory Data with Character Results		SAC
21.	Safety	LIVER5	Listing of Liver Monitoring/Stopping Event Reporting		
22.	Safety	LIVER13	Listing of Subjects Meeting Hepatobiliary Laboratory Criteria Post-Baseline		
ECG					
23.	Safety	EG3	Listing of ECG Values (Participants with QTcF >500 msec or Increase > 60 msec from Baseline)		SAC
24.	Safety	EG5	Listing of Abnormal ECG Findings	IDSL	SAC

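### Three safety summaries promised in Protocol 9.4.2 have no table in the SAP and no recorded removal, and the AESI tables stop 28 days after the last dose

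*Protocol*

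**What the plan says.** Protocol 9.4.2 (Safety Analyses) makes two commitments. By phase: "SAEs occurring pre-treatment and AEs and SAEs occurring during active treatment and post-treatment will be summarized separately". By type: "Separate summaries will be provided for all AEs, investigational product-related AEs, SAEs, AEs of special interest", and also "for AEs leading to permanent discontinuation of investigational product or withdrawal from the study".

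SAP 2.2.2 lists what will be reported after the futility termination. It keeps the safety objective and its AE endpoint as they were. SAP 8.1 leaves the detail of the AE displays to Appendix 9, so that list is what will be programmed. It includes tables such as "Summary of Post-Treatment Serious Adverse Events by System Organ Class and Preferred Term" and "Summary of On-Treatment Adverse Events of Special Interest Categorised as Opportunistic Infections". For AEs that end treatment or participation it offers "Listing of Adverse Events Leading to Withdrawal from Study / Permanent Discontinuation of Study Treatment", which is Listing 15.

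SAP 8.2 calls for an AESI summary table once one event is reported in a category, but makes AESI listings conditional: "if more than one event is reported under each AESI category". The note to Listing 17 in Appendix 9 uses a different trigger, more than one AESI overall.

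On never-dosed subjects, Protocol 5.3 says that "a minimal set of screen failure information is required including Demography, Screen Failure details, Eligibility Criteria, and Serious Adverse Events".

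**The concern.** A reader comparing the protocol with the clinical study report would expect each promised summary, or a recorded reason for its absence. If the SAP is followed as written, product-related AEs are not tabulated by arm, and neither are the events that led to discontinuation.

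Pre-treatment SAEs have no summary. Protocol 7.4.1.1 collects SAEs from consent when they are related to study participation, including to a change in existing therapy, or to a sponsor product. Such an event in a subject who is never dosed would be collected and then displayed nowhere.

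AESIs are grouped and counted only up to 28 days after the last dose, although AE collection continues for 8 weeks. Protocol 4.6.1 itself notes that delayed as well as acute systemic reactions have been reported with this product.

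**Working it through.** There is no planned figure to reproduce. The check sets the commitments against the display list and then works out the AESI window.

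**Commitment against display (SAP 12.9.4, 12.9.6 and 12.9.12)**

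| Protocol 9.4.2 commitment | SAP table | Other SAP display |
|---|---|---|
| All AEs, during and after treatment | 3.1, 3.2 | Listing 12 |
| SAEs, during and after treatment | 3.6, 3.7 (3.8 for fatal) | Listing 12 |
| Pre-treatment SAEs | none | Listing 12, dosed subjects only |
| Product-related AEs | none | a row in the AESI profile shell (SAF_T2) only |
| AEs leading to discontinuation or withdrawal | none | Listing 15; reasons, without AE terms, in Tables 1.1 and 1.2 |
| AESIs | 3.9 to 3.26, all titled on-treatment | Listing 17, if more than one AESI |

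The last three columns of evidence to note are these:

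- SAP 12.3.1 defines a pre-treatment phase, but no AE table uses it.
- SAP 4 defines an All Screened population, but assigns it only to study-population displays. Every AE table and listing uses the Safety population, which requires at least one dose.
- SAP Table 1 records even the change of wording from subjects to participants. It has no entry for any AE, SAE or AESI summary.

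**AESI window**

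Inputs: doses every 28 days from Day 1 (Protocol 4.2.2); on-treatment days = (last dose − first dose) + 29 (SAP 12.5.2); AE collection to the visit 8 weeks after the last dose (Protocol 4.2.3 and 7.4.1.1), with a window of ±3 days (Protocol Table 3).

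Four doses:

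- Last dose on Day 3 × 28 + 1 = 85.
- On-treatment to Day (85 − 1) + 29 = 113.
- AE collection to Day 85 + 56 = 141 (138 to 144).
- Outside the AESI tables: 141 − 113 = 28 days (25 to 31).
- Share of follow-up after the last dose: 28/56 = 50% (25/53 = 47% to 31/59 = 53%).
- Share of all AE collection: 28/141 = 20% (25/138 = 18% to 31/144 = 22%).

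One dose, then both post-treatment visits: on-treatment to Day 29, collection to Day 57, gap 28 days, or 28/57 = 49% of AE collection (25/54 = 46% to 31/60 = 52%).

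**What happens to an AESI after that window**

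In a dosed subject it is counted by preferred term in Table 3.2, in Table 3.7 if serious, and appears in Listing 12. None of these groups events as AESIs. Listing 17 has no phase limit, but if this is the only AESI in the study, neither its Appendix 9 note nor the per-category wording in SAP 8.2 triggers it.

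**The case against.** The strongest reply is that little is lost. For dosed subjects the data are in Listing 12, discontinuation events are in Listing 15, reasons for stopping are tabulated in Tables 1.1 and 1.2, and late events are counted in Tables 3.2 and 3.7. The trial stopped for futility and its safety analysis is descriptive. Protocol 9.4.2 also leaves full details of the safety analyses to the reporting and analysis plan. Most of this stands, and it makes the point one about summaries rather than data. It does not cover the three missing tables. Leaving details to a later document is not the same as removing a named summary, and the reduced scope after termination does not reach an endpoint that SAP 2.2.2 retains.

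The AE shells follow sponsor standards that are not reproduced in the SAP, so whether any of them shows relatedness cannot be checked. A relatedness column in a listing would still not be a by-arm table.

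Some stronger readings are tempting but not supported:

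- A reader might infer that post-treatment AESI tables are expressly promised. They are not. The expectation follows from the sentence on separate phases, together with SAP 8.2 setting no phase limit. The limit comes only from the titles in Appendix 9.
- A reader might infer that a single anaphylaxis would go unreported. Under SAP 8.2 one on-treatment event is enough for its summary table, and it is also in Table 3.1 and Listing 12. The protocol promises no profile table, so its absence for a single event is not a defect.
- A reader might size the never-dosed group from the planned screening and randomisation numbers, or from the longest washout. The planned numbers are for full enrolment, which did not occur. The longest washout applies only to subjects stopping a biologic. Only related SAEs are collected before treatment. Protocol 5.3 requires collection and does not itself promise an analysis of screen failures.

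**Conclusion.** The point holds as a gap in planned summaries and in the record of changes. Three summaries named in Protocol 9.4.2 have no table and no entry in SAP Table 1. All 18 AESI tables (18 of 18) are limited to the on-treatment phase, which leaves 28 days (25 to 31) per subject outside them, half of the planned follow-up after the last dose. This assumes dosing and visits on schedule and follow-up to the second post-treatment visit.

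Two kinds of event lack an adequate display: an SAE in a consented but never-dosed subject, which has none, and a lone late AESI, which is not shown as one. The documents give no rate for either, so the number of events affected cannot be estimated and may be zero. It would be wrong to say that the safety objective goes unreported: overall AE and SAE incidence and on-treatment systemic and injection-site reactions are all tabulated. The change is worth making because the protocol commits to these summaries and the data are already collected.

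**What to change.** In SAP 12.9.6, add by-arm tables by system organ class and preferred term for product-related AEs and for AEs leading to permanent discontinuation or withdrawal. Add a pre-treatment SAE summary or listing on the All Screened population. Add a post-treatment column to the AESI summary tables (the SAF_T1 displays among Tables 3.9 to 3.25). Produce Listing 17 when at least one AESI is reported, and make its note agree with the wording in SAP 8.2. If any of these summaries is being dropped on purpose, record it in SAP Table 1 with the reason.

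The cost is SAP wording and a few standard displays from data already collected. Some may be empty.

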9.4.3. Exploratory Analyses

Pharmacokinetic Analyses

Blood samples will be collected to determine mepolizumab plasma concentrations as per the Time and Events Table (Table 3).

Sparse blood sampling is being implemented in this study and mepolizumab plasma concentrations will be analyzed by population PK methods using the current population PK model in order to determine, for example, the subject's individual systemic exposure, and apparent clearance. In addition to the covariates already included in the current population PK model, the effect on mepolizumab systemic exposure of other covariates of particular interest in subjects with AD may be explored if deemed appropriate. Furthermore, the model will be used to generate predictions against which the model will be validated prospectively using the observed data from the study (sparse sampling) in order to confirm the absence of AD disease impact on mepolizumab exposure. The ability of the model to describe data in AD subjects will be assessed by prospective validation using appropriate goodness of fit tests.

Pharmacokinetic data will be presented in graphical and/or tabular form and will be summarized descriptively. Full details of the analysis to be performed will be given in the RAP.

Pharmacodynamic (PD) Analyses

PD endpoints are defined in Section 3. Full details of planned analyses of PD endpoints will be included in the RAP.

Patient-Reported Outcomes (PRO) Endpoints

PRO endpoints are defined in Section 3. Full details of planned analyses of PRO

endpoints will be included in the RAP and/or a separate PRO RAP.

Efficacy Endpoints

“Exploratory” efficacy endpoints are defined in Section 3. Full details of the planned analysis of all “Exploratory” efficacy endpoints will be included in the RAP.

EASI: The proportion of subjects with cutpoints (e.g., -50%, -75%) for percent change from baseline will be summarized by visit. Point-estimates and 90% confidence intervals for the differences between the experimental and vehicle arm at Week 16 will be presented. No formal hypothesis testing will be performed.

Itch (Daily Sign and Symptom Severity Diary NRS Question #1): Subject’s change from baseline/percent change from baseline in weekly average and the 90% confidence interval for the difference between the experimental and vehicle arm at Week 16 will be presented. No formal hypothesis testing will be performed.

Itch (Daily Sign and Symptom Severity Diary NRS Question #1): Subject’s change from baseline/percent change from baseline and the proportion of subjects with cutpoints (e.g., -50%, -75%) for percent change from baseline will be summarized by visit.

Disease Flare/Relapse Endpoints

Disease flare/relapse endpoints are defined in Section 3. Full details of the planned analysis of these endpoints will be included in the RAP.

Relationship between Efficacy and Blood Eosinophils

Endpoints to characterize the relationship between efficacy and blood eosinophil counts are described in Section 3.

If data permits, EASI percent change from baseline will be analyzed using a Mixed Model Repeated Measures (MMRM) analysis, fitting subject as a random effect, and baseline value, treatment group and baseline blood eosinophil count as fixed effects. An unstructured variance-covariance matrix structure will be assumed.

Further exploratory analyses to determine the impact of baseline blood eosinophils may be conducted.

Full details of the planned analysis of these endpoints will be included in the RAP.

10. STUDY GOVERNANCE CONSIDERATIONS

10.1. Posting of Information on Publicly Available Clinical Trial Registers

Study information from this protocol will be posted on publicly available clinical trial registers before enrollment of subjects begins.

10.2. Regulatory and Ethical Considerations, Including the Informed Consent Process

Prior to initiation of a site, GSK will obtain favorable opinion/approval from the appropriate regulatory agency to conduct the study in accordance with ICH Good Clinical Practice (GCP) and applicable country-specific regulatory requirements.

The study will be conducted in accordance with all applicable regulatory requirements, and with GSK policy.

The study will also be conducted in accordance with ICH Good Clinical Practice (GCP), all applicable subject privacy requirements, and the guiding principles of the current version of the Declaration of Helsinki. This includes, but is not limited to, the following:

- IRB/IEC review and favorable opinion/approval of the study protocol and amendments as applicable
- Obtaining signed informed consent
- Investigator reporting requirements (e.g., reporting of AEs/SAEs/protocol deviations to IRB/IEC).
- GSK will provide full details of the above procedures, either verbally, in writing, or both.
- Signed informed consent must be obtained for each subject prior to participation in the study.
- The IEC/IRB, and where applicable the regulatory authority, approve the clinical protocol and all optional assessments, including genetic research.
- Optional assessments (including those in a separate protocol and/or under separate informed consent) and the clinical protocol should be concurrently submitted for approval unless regulation requires separate submission.
- Approval of the optional assessments may occur after approval is granted for the clinical protocol where required by regulatory authorities. In this situation, written approval of the clinical protocol should state that approval of optional assessments is being deferred and the study, with the exception of the optional assessments, can be initiated.

